## INTRODUCTION

Diabetic foot ulcers need complex treatment and have poor prognoses. Thus, they consume medical resources and impede patients' quality of life. Most of the time, patients are required to perform diabetic foot ulcer self-management at home. However, their self-management behaviors are inadequate.

Individualized patient education messages can promote and maintain appropriate diabetes self-management behaviors. The short message-based customized standardized patient education program combines several smartphone message-based standardized educational contents to construct a customized patient education program that is according to patients' needs, thus promptly providing individualized patient education. The short message-based customized standardized patient education program may improve diabetic foot ulcer self-management behavior and self-efficacy on diabetic foot ulcer self-management, thereby promoting wound healing and improving quality of life.

This study aims to develop a short, message-based, customized standardized education program and to test the effect of the program on diabetic foot ulcer self-management behavior, self-efficacy, wound prognosis, and quality of life.

## 2. METHODS

### 2.1 Study design

A customized standardized patient education module will be developed and evaluated. A randomized controlled study design will be adopted.

Participants will be assigned to two parallel groups for the duration of the study.

## 2.2 Study setting and participants

The participants will be recruited from August 2023 to July 2026 and followed up for eight weeks at a medical center in northern Taiwan.

Recruited criteria were: (1) outpatients with DFUs over 20 years old; (2) can be interviewed in Mandarin or Taiwanese.

The exclusion criteria were: patients (1) planning to return visits within eight weeks less than two times; (2) without using a smartphone; (3) being unable to read text messages on a mobile phone or with impaired hearing; (4) with impaired fine hand movements; (5) unwilling to use the communication software LINE to receive text messages.

## 2.3 Sample size and statistical power

In this study, we will use the generalized estimating equation (GEE) to detect the effectiveness of intervention in improving the quality of life. Since no previous research results are available for reference, we assume that the intervention in this study has a moderate effect. We set the effect amount as 0.25, the statistical power as 0.95, the alpha value as 0.05, and the number of repeated measurements as 3. The G\*power 3.1 statistical software shows that the required sample size was 178.

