### 2.6.3 Diabetes-related Foot Ulcer Quality of Life

A questionnaire on quality of life with chronic wounds (Wound QoL-14) will be used to evaluate the change in QOL. The questionnaire on quality of life with chronic wounds (Wound-QoL) has 14 items to measure patients' quality of life with chronic wounds. Using the 5-point Likert scale, the influence of chronic wounds in the past seven days ranges from 0 (not at all) to 4 (significantly affected), with higher scores indicating poorer quality of life. The range of scores is 0 to 56.

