## 2.7 Data collection

Before the study delivery, we will perform block randomization of four categories according to the statistical software (Sealed Envelope Ltd., 2022), with four as the block, and create label categories and case acceptance order according to the software allocation group, then putting the group name into the envelope. This study adopted categorical random allocation, with four categories: patients with neuropathic foot ulcers who received hemodialysis, patients with neuropathic foot ulcers who did not receive hemodialysis, patients without neuropathic foot ulcers who received hemodialysis, patients without neuropathic foot ulcers who did not receive hemodialysis.

After the research subjects agree to participate, the project leader will open envelopes to arrange their group location. Then, the data collection begins, including basic information on the research subjects, self-care behavior for diabetes, foot, and diabetic foot ulcers, self-efficacy in preventing and treating foot ulcers, quality of life, and wound measurement. Two post-tests (questionnaire interview and wound

assessment) will be conducted four and eight weeks after baseline data collection.

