## 2.8 Data analysis

The data will be analyzed with SPSS statistical software for Windows 20.0 (SPSS, Inc., Chicago, IL, USA). The chi-square and Mann-Whitney U tests will be used to determine the homogeneity between the intervention and control groups. An intention-to-treat analysis approach (ITT) will be used. Generalized estimating equations (GEEs) will be used to examine the effects of intervention measures on improving the study subjects' self-care behavior, self-efficacy, and quality of life. The chi-square test will be used to detect whether there was any difference in the proportion of wounds reduced by 50% or more between the two groups of study subjects four weeks after admission.

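### The 95% power for quality of life is attached to no stated GEE contrast, although one of the three measurements is a baseline, and the stated inputs alone do not give 178

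*Combined protocol and SAP*

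**What the plan says.** - **Section 2.3** states the purpose of the sample size: "we will use the generalized estimating equation (GEE) to detect the effectiveness of intervention in improving the quality of life". It calls the assumed effect moderate, sets it at 0.25, and adds "the statistical power as 0.95, the alpha value as 0.05, and the number of repeated measurements as 3". It concludes that the G\*Power 3.1 "statistical software shows that the required sample size was 178". It gives no G\*Power routine, effect-size metric, within-person correlation or loss allowance.
- **Section 2.6.3** says that the Wound-QoL questionnaire "will be used to evaluate the change in QOL".
- **Section 2.7** includes "self-efficacy in preventing and treating foot ulcers, quality of life, and wound measurement" in the baseline data, and the two post-tests "will be conducted four and eight weeks after baseline data collection". The three measurements are therefore baseline, week 4 and week 8. On the order of events it says that "the project leader will open envelopes to arrange their group location. Then, the data collection begins".
- **Section 2.8** says that GEEs "will be used to examine the effects of intervention measures on improving the study" subjects' self-care behaviour, self-efficacy and quality of life. It names no model term, time point or covariate.

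**The concern.** A power figure belongs to a particular test. A GEE with two groups and three visits offers several tests of the intervention: a group effect over all visits, a group-by-time interaction, a week-8 difference, or a post-baseline difference adjusted for baseline. Randomisation makes the expected group difference zero at baseline, so these tests use the same data with different efficiency. A test that averages over baseline dilutes a later effect.

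While the choice is open, a null result cannot be read against a known power, and the test could be chosen after the data are seen. There is also a smaller reporting gap: a reader cannot reproduce 178 from the inputs listed.

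**Working it through.** **Inputs from the plan:** effect 0.25, power 0.95, alpha 0.05, three measurements, total 178 (2.3); two parallel groups (2.1); baseline, week 4 and week 8 (2.7).

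**Assumptions, not in the plan:** 0.25 is Cohen's f, which is d = 2 × 0.25 = 0.5 SD for two equal groups; 1:1 allocation; two-sided alpha; equal correlation ρ between all pairs of visits.

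**Step 1: trying to reproduce 178.** Noncentral F, f² = 0.0625, m = 3 measurements, two groups.

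- Between factors: λ = f²·N·m / (1 + (m−1)ρ), df (1, N−2). At ρ = 0.5, λ = 0.0625 × N × 3 / 2, and 95% power needs N = 142.
- Within-between interaction: λ = f²·N·m / (1−ρ), df (2, 2(N−2)). At ρ = 0.5, N = 44.
- Interaction with the SPSS-type effect size: λ = f²·(N−2)·(m−1)·ε. With ε = 1, N = 128.

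None of these gives 178. Each route found to 178 needs an input that the plan does not report:

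- between factors at ρ = 0.5 with a 20% loss allowance: 142 / 0.8 = 177.5, rounded up to 178;
- between factors with ρ of about 0.76 to 0.77;
- the SPSS-type interaction with ε of about 0.64.

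**Step 2: power by contrast.** Assumed pattern: a difference of 0 at baseline and 0.5 SD at weeks 4 and 8. With n per arm and SD = 1, the variance of each estimated difference is:

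- baseline-adjusted average of weeks 4 and 8: (2/n)·[(1+ρ)/2 − ρ²];
- week 8, baseline-adjusted: 2(1−ρ²)/n;
- week-8 change from baseline: 4(1−ρ)/n;
- average over all three visits: (2/n)·(1+2ρ)/3, where the difference shrinks to (0 + 0.5 + 0.5)/3 = 0.333 SD.

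The 2-df group-by-time test uses a noncentral F with df (2, 2(N−2)).

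Example: adjusted average, n = 89, ρ = 0.5. Variance = (2/89)(0.75 − 0.25) = 0.01124, SE = 0.106, 0.5/0.106 = 4.72, power 99.7%.

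| Contrast, 178 analysed | ρ = 0.3 | ρ = 0.5 | ρ = 0.7 |
|---|---|---|---|
| Weeks 4 and 8 averaged, adjusted | 99.3% | 99.7% | 99.98% |
| Week 8, adjusted | 94% | 97% | 99.6% |
| 2-df group-by-time | 84% | 94% | 99.6% |
| Week-8 change | 80% | 91% | 99% |
| Group effect over all three visits | 86% | 77% | 70% |

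**Step 3: sensitivity of the most powerful contrast.** With 142 analysed (178 less an illustrative 20%), the adjusted average has 97.7% / 98.7% / 99.9%. If instead the effect builds up, 0.25 SD at week 4 and 0.5 SD at week 8 (also assumed), the averaged difference is 0.375 SD. Power is then 91% / 94% / 99% with 178 analysed and 84% / 88% / 96% with 142. In the same build-up case, the week-8 adjusted contrast with 178 keeps 94% / 97% / 99.6%.

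**The case against.** The strongest reply is that the figures below 95% come from a pattern that the plan never states. If f = 0.25 is entered as the standardised size of the tested effect itself, 178 gives 99.5% / 98.2% / 96.0% for the between-group effect at correlations 0.3 / 0.5 / 0.7, and more than 99.9% for the default within-between interaction. Under the pattern in Step 2, f is only 0.167 for the three-visit effect (0.333/2) and 0.118 for the interaction. This stands as a limit on the numbers, which are conditional on that pattern. It does not remove the gap, because 2.3 does not say which effect the 0.25 describes, and a zero expected difference at baseline follows from randomisation.

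A reader might infer that the plan tests a group effect averaged over baseline and so has only 70% to 86% power. The documents do not support that. The wording on change in 2.6.3 and on improvement in 2.8 points, if anything, to a change or group-by-time test. A between-factors calculation is one way to reach 178, but that the sponsor used it is conjecture.

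It is also fair to say that group-by-time, week-8 and averaged contrasts are all defensible. The need is to fix one in advance, and the choice between average and week 8 belongs to the sponsor.

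**Conclusion.** The concern holds as a gap in specification. The 95% is attached to no defined test. For the assumed effect of 0.5 SD at both post-tests, the contrasts left open range from 70% to nearly 100% power with the same 178 patients. These figures rest on reading 0.25 as Cohen's f, equal correlation between visits, 1:1 allocation and 178 analysed.

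Two stronger readings are tempting and should not be drawn. The first is that 178 is wrong or too small: failure to reproduce it from the listed inputs shows incomplete reporting only, and 142 with a 20% loss allowance matches it exactly, though neither is documented. The second is that a baseline-adjusted contrast secures 95%: the adjusted average exceeds 95% if the effect is full by week 4, but falls to 91% at correlation 0.3 with 178, or 84% with 142, if the effect builds up.

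This should be fixed. Confidence is high on the omission and conditional on the assumptions for the size.

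**What to change.** Keep 178.

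- **Section 2.8:** test the intervention on Wound-QoL with one pre-specified post-baseline GEE contrast, either the average of weeks 4 and 8 or week 8 alone, with baseline Wound-QoL as a covariate. Do not use a group effect averaged over baseline.
- **Section 2.7:** record baseline Wound-QoL before the envelope is opened, so that a self-reported covariate cannot reflect knowledge of the group. Section 2.2 dates recruitment from August 2023, so for patients already enrolled, note which order was used.
- **Section 2.3:** tie the power to the chosen contrast and give it over correlations 0.3 to 0.7. State the effect metric and assumed pattern, the G\*Power routine, the correlation, any sphericity value or loss allowance, and whether 178 means enrolled or analysed patients.

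Cost: a few sentences in 2.3, 2.7 and 2.8 and a change in the order of baseline collection, with no extra patients, visits or measurements. Averaging dilutes an effect that appears late (94% against 97% for week 8 adjusted, at correlation 0.5 in the build-up example). The stated power may become slightly less favourable than 95%.

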## 2.4 Intervention group

At each visit of the research subjects to the plastic clinic, the research team records the attending prescriptions and patient education given by the medical team members and evaluates whether the research subjects and caregivers need additional mental support. Then, according to the

above evaluation and records, items of a designed patient education menu will be selected, and the selected patient education messages will be sent according to the transmission frequency and period proposed by the research subject

## 2.5 Control group

Subjects will receive routine care.

## 2.6 Measurements

### 2.6.1 Sociodemographic and clinical information

This study collected data by foot assessment, medical record review, and questionnaire interviews.

### 2.6.2 Whether the Wound Shrinks

This study will measure the wound size at baseline, four and eight weeks. Then, whether the wound has shrunk will be determined by subtracting the pre-measurement area from the post-measurement area.

### 2.6.3 Diabetes-related Foot Ulcer Quality of Life

A questionnaire on quality of life with chronic wounds (Wound QoL-14) will be used to evaluate the change in QOL. The questionnaire on quality of life with chronic wounds (Wound-QoL) has 14 items to measure patients' quality of life with chronic wounds. Using the 5-point Likert scale, the influence of chronic wounds in the past seven days ranges from 0 (not at all) to 4 (significantly affected), with higher scores indicating poorer quality of life. The range of scores is 0 to 56.

### 2.6.4 Diabetes-related foot ulcer self-management behavior

In this study, Chin et al. (2019) used the Diabetes-related Foot Ulcer Self-Management Behavior Scale (DFUSMB) to measure DFU

self-management behavior. The DFUSMB measures behaviors that promote wound healing and prevent wound deterioration with 18 items in total, using the five-point Likert scale. "Never," "Seldom," "Sometimes," "Often," and "Always" are scored from 1 to 5, respectively. Reverse questions are scored in reverse. The higher the total score, the better the self-management behavior. The DFUSMB has sufficient reliability and validity (Chin et al., 2019).

#### 2.6.5 Diabetes-related Foot Ulcer Self-management Self-efficacy

We used 11 questions to measure the diabetes-related foot ulcer self-management self-efficacy, using an 11-point scale, with 0 indicating no confidence and 10 indicating complete confidence. The high scores reflect high self-efficacy. The sum score of the above 11 items indicates the DFU self-management self-efficacy with a range from 0 to 110.

#### 2.6.6 Diabetes-related foot self-care behavior

This study used Chin & Huang's (2013) Diabetes-related Foot Self-Care Behavior Scale (DFSBS) to measure participants' diabetes-related foot-care behavior. The DFSBS has seven questions measuring the frequency of foot care behaviors delivery. The higher the score, the better the foot care behavior. The DFSBS has sufficient reliability and validity (Chin & Huang, 2013).

#### 2.6.7 Diabetes self-care behaviors

In this study, the summary of the diabetes self-care activity questionnaire (SDSCA) will be used. Deborah Toobert developed the SDSCA questionnaire. It focuses on general diet, diabetes-specific diet, physical activity, blood-glucose testing, foot care, and smoking. The instrument

assesses the absolute frequency or consistency of ten diabetes health-related regimen behaviors (e.g., number of days per week on which respondents engage in physical activity sessions; number of days in the past 7 days respondents ate five or more servings of fruits and vegetables). Reverse questions are scored in reverse, and the higher the total score, the better the diabetes self-care activity. The total SDSCA score ranges from 1-63.

## 2.7 Data collection

Before the study delivery, we will perform block randomization of four categories according to the statistical software (Sealed Envelope Ltd., 2022), with four as the block, and create label categories and case acceptance order according to the software allocation group, then putting the group name into the envelope. This study adopted categorical random allocation, with four categories: patients with neuropathic foot ulcers who received hemodialysis, patients with neuropathic foot ulcers who did not receive hemodialysis, patients without neuropathic foot ulcers who received hemodialysis, patients without neuropathic foot ulcers who did not receive hemodialysis.

After the research subjects agree to participate, the project leader will open envelopes to arrange their group location. Then, the data collection begins, including basic information on the research subjects, self-care behavior for diabetes, foot, and diabetic foot ulcers, self-efficacy in preventing and treating foot ulcers, quality of life, and wound measurement. Two post-tests (questionnaire interview and wound

assessment) will be conducted four and eight weeks after baseline data collection.

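### A single block size of four in each stratum, at one centre with no blinding described, could let anyone tracking allocations know up to about one in three in advance; varying the block size is a cheap improvement

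*Combined protocol and SAP*

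**What the plan says.** Section 2.7 (Data collection) specifies stratified block randomisation. "This study adopted categorical random allocation, with four categories", formed by crossing neuropathic ulcer (yes/no) with hemodialysis (yes/no). One block size is given, "with four as the block", and no variation in it is described. The list is prepared before the study starts, "then putting the group name into the envelope". Once a patient has agreed to take part, "the project leader will open envelopes to arrange their group location". The section does not say who holds the list, or whether the block size is kept from those who enrol.

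Section 2.1 describes two arms: "Participants will be assigned to two parallel groups for the duration of the study". The allocation ratio is not stated. Section 2.2 places the whole trial "at a medical center in northern Taiwan", with recruitment from August 2023 to July 2026.

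No section mentions blinding. Under section 2.4, in the intervention arm "the selected patient education messages will be sent according to the transmission frequency and period proposed by the research subject". Under section 2.5, the control arm has routine care, with no dummy messages.

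**The concern.** When the block size is constant and known, the end of each block gives itself away. Once two patients in a block of four have gone to the same arm, the last two must go to the other. Once three have been allocated, the fourth is fixed. Stratification does not remove this; the observer simply needs four tallies instead of one. With one centre and visible treatment, all the information for those tallies collects in one place.

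At stake is who enters which arm. Someone with advance knowledge and a say in recruitment could approach a motivated patient, or one with a promising ulcer, when the next allocation suits, or wait until a later visit. Waiting is practical here, because section 2.2 excludes patients planning fewer than two return visits in eight weeks. Quality of life, self-management behaviour and self-efficacy are self-reported, and wound reduction depends on the ulcer at entry, so such selection could affect all of them. Section 2.7 also starts baseline data collection after the envelope is opened, so baseline comparisons would be an imperfect check.

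**Working it through.** The plan gives no figure for predictability, so there is none to reproduce.

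**Inputs**
- Block size 4, four strata: section 2.7.
- Two arms: section 2.1. A 1:1 ratio is an assumption.
- Total of 178 patients: section 2.3, used only to turn shares into counts.
- An observer who knows the block size and every past allocation in each stratum: an assumption, and the worst case.

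**Certain knowledge, blocks of four.** There are six equally likely sequences: AABB, ABAB, ABBA, BAAB, BABA, BBAA. An allocation is known when all remaining places in the block belong to one arm.
- Places 1 and 2: never known.
- Place 3: known when the first two agree, 2/6 = 1/3.
- Place 4: always known.
- Average: (0 + 0 + 1/3 + 1)/4 = 33.3%.

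If every block were complete, this would be 178/3 = 59 allocations. Each stratum may end on an incomplete block. Simulating 178 patients over four strata, under three different stratum mixes, gives 32.4% on average (range 31.8% to 33.0%), or 0.324 × 178 = 58 allocations.

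**Best guess, blocks of four.** The observer names the arm with more places left.
- Place 1: 1/2.
- Place 2: 2/3.
- Place 3: (1/3 × 1) + (2/3 × 1/2) = 2/3.
- Place 4: 1.
- Average: (1/2 + 2/3 + 2/3 + 1)/4 = 70.8%, against 50% by chance.

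**The 1:1 assumption.** With two arms, a block of four could also hold a 3:1 split. The share known for certain would then be (0 + 0.25 + 0.5 + 1)/4 = 43.75%. Assuming 1:1 does not inflate the result.

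**Alternatives, by enumeration or simulation (1:1).** In the mixed case the observer knows the possible sizes but not their order, and there are about 45 patients per stratum.

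| Scheme | Known for certain | Best guess correct |
|---|---|---|
| Fixed 4 | 33.3% | 70.8% |
| Fixed 6 | 25% | 68.3% |
| Fixed 8 | 20% | 66.6% |
| Random 4 and 6 | about 6% (runs gave 5.4% to 5.9%) | about 69% |

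For random 4 and 6, the count known for certain is between 0.054 × 178 = 10 and 0.059 × 178 = 11 allocations, compared with 58. The best guess improves much less: its excess over chance goes from 70.8 − 50 = 20.8 points to about 68.8 − 50 = 18.8 points, roughly a tenth less.

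**The case against.** A fixed block of four is a complete and clearly reported method. It contradicts nothing else in the plan, and preferring varied blocks is a recommendation, not the correction of an error. That stands, and is why this is labelled a cheap improvement.

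A reader might infer that the project leader knows the next allocation before approaching a patient and can act on it. The documents do not support that. Section 2.7 has the envelope opened only after agreement, so the only route to bias is who is approached and when, and no section says who screens, approaches or consents patients. If a person who does not follow the allocations does this, the opener's knowledge cannot affect entry.

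A reader might also take it that the stratum is known at screening. It must be known before an envelope is chosen, but nothing says it is known before the approach. Treatment being open is likewise an inference, though a fair one given messages against routine care. And one in three needs an accurate tally in four strata over three years, so it is an upper figure.

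The strongest point concerns the remedy. Selective enrolment can work on a good guess, and the guess rate hardly moves. The larger safeguard is concealment: who makes and holds the list, and how the envelopes are protected. That also stands, and limits what is claimed for the change. Simply deleting the block size from the protocol would do little, since the team may already know it.

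**Conclusion.** The point holds as a conditional one. With 1:1 blocks of four, an observer who tracks each stratum could know up to about one in three allocations (about 58 of 178) for certain before the envelope is opened, and guess about 71% correctly. This rests on the assumed ratio, on treatment being visible, and on complete tracking by stratum.

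It becomes a route to selective enrolment only if that person, who might be the project leader, also influences who is approached or when. The documents leave this open. It would be tempting to conclude that the outcomes will be biased, but the documents show only that foreknowledge is possible. They do not show that selection occurs, and no effect on any outcome has been estimated.

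**What to change.** For the unused part of the list, generate a new sequence with randomly ordered block sizes (for example 4 and 6) within each of the four strata. Have the sizes and their order held only by whoever prepares the envelopes, and not by anyone who screens, approaches or enrols patients. Section 2.7 needs one sentence saying that block sizes vary at random and that those who enrol do not have them. Naming the role that approaches patients in the same place would settle the condition on which the concern depends.

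The cost is regenerating the remaining list and preparing new envelopes. The largest possible imbalance from an unfinished last block rises from 2 to 3 in a stratum, so the worst case over four strata goes from 4 × 2 = 8 to 4 × 3 = 12 patients. The change should sit beside proper allocation concealment and not stand in for it. If enrolment has already finished, report the fixed block size, and who knew it, as a limitation.

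### Section 2.7 opens the allocation envelope before the outcome baselines are collected, and no blinding is described, so baseline self-reports and wound area may be recorded with the arm known

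*Combined protocol and SAP*

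**What the plan says.** Section 2.7 (Data collection) gives the sequence in two sentences. Once a patient has agreed to take part, "the project leader will open envelopes to arrange their group location. Then, the data collection begins". The collection covers basic information and the self-care behaviour measures, and the list continues with "self-efficacy in preventing and treating foot ulcers, quality of life, and wound measurement". The two post-tests "will be conducted four and eight weeks after baseline data collection", so the collection that follows the envelope is the trial's baseline.

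That baseline is used in two ways:

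- **Wound outcome.** Section 2.6.2 judges shrinkage by "subtracting the pre-measurement area from the post-measurement area". Section 2.8 (Data analysis) uses a chi-square test for any "difference in the proportion of wounds reduced by 50% or more between the two groups" at four weeks.
- **Questionnaire outcomes.** Section 2.8 analyses self-care behaviour, self-efficacy and quality of life by GEE without listing model terms. Section 2.3 gives "the number of repeated measurements as 3", which matches baseline, week 4 and week 8.

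No section of the available text mentions blinding of patients, interviewers, wound assessors or analysts, or says that the allocation is withheld until baseline is complete.

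**The concern.** A baseline measurement is protected from the allocation only if it is taken before anyone involved can know the arm. Here the written order is the reverse. The measurements are also of the kind that knowledge can influence: section 2.6.1 describes interviews and foot assessment alongside record review, and the scales in 2.6.3 to 2.6.7 are self-reported. The control arm gets routine care (2.5), with no dummy messages described. Intervention patients propose the frequency and period of their messages (2.4), so they must learn their arm at some point; the plan does not say when.

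If knowing the arm moves a baseline answer or an area reading, the error passes into the treatment comparison. The direction cannot be predicted. The homogeneity tests in 2.8 could not settle the matter, because a difference in outcome baselines recorded after allocation may be chance or reporting.

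**Working it through.** **1. Order of steps.** The sequence in 2.7 is consent, envelope, outcome baselines, then post-tests timed from those baselines. Only the stratum data (neuropathic ulcer or not, hemodialysis or not) must be known earlier, to choose the right envelope, and these are not outcomes. Section 2.6.2 schedules a wound measurement at baseline but does not place it before the envelope. Nothing else in the plan puts the baseline earlier.

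**2. Inputs for the illustration.** From the documents: N = 178 (2.3), taken as the number analysed; the 50% threshold and the four-week time point (2.8). Assumed: 1:1 allocation, outcome SD 1, visit correlation ρ = 0.5 (range 0.3 to 0.7), no true effect, and a shift of s SD in one arm at baseline but not at follow-up. The documents give no size or direction for s.

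**3. Questionnaire scores.** The probability of a false positive is Φ(b/SE − 1.96) + Φ(−b/SE − 1.96), where b is the size of the bias. It depends on the effect that the GEE tests, which 2.8 leaves open:

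- Change from baseline to week 8: b = s, SE = √[(4/178) × 2(1 − ρ)] = 0.177, 0.150, 0.116 for ρ = 0.3, 0.5, 0.7.
- Follow-up adjusted for baseline: b = ρs, SE = √[(4/178)(1 − ρ²)] = 0.143, 0.130, 0.107.
- Group effect averaged over all three visits: b = s/3, with the opposite sign to the change-score bias, SE = √[(4/178)(1 + 2ρ)/3] = 0.110, 0.122, 0.134.
- Follow-up values only: b = 0, and the error rate stays at 0.05.

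At ρ = 0.5 and s = 0.1, the change score has b/SE = 0.1/0.150 = 0.67, which gives 0.102.

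| Effect tested | s = 0.1; ρ = 0.3, 0.5, 0.7 | s = 0.2; ρ = 0.3, 0.5, 0.7 |
|---|---|---|
| Change from baseline | 0.087, 0.102, 0.138 | 0.204, 0.266, 0.406 |
| Adjusted for baseline | 0.055, 0.067, 0.100 | 0.070, 0.120, 0.258 |
| Average over three visits | 0.061, 0.059, 0.057 | 0.093, 0.085, 0.079 |

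**4. Wound endpoint.** If baseline area is read k times too large, a recorded 50% reduction corresponds to a true reduction of 1 − 0.5k: 47.5% for k = 1.05 and 45% for k = 1.10. To turn this into a difference between arms, assume that 40% truly reach the threshold in both arms, that the log of the week 4 to baseline area ratio is normal with SD σ = 0.8 (range 0.5 to 1.0), and that there are 89 patients per arm. The apparent rate in the affected arm is Φ(Φ⁻¹(0.40) + ln k/σ). For k = 1.10 and σ = 0.8 this is Φ(−0.253 + 0.0953/0.8) = Φ(−0.134) = 0.447. Type I error is from a two-proportion z test.

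| Baseline read high by | Apparent rate; σ = 0.5, 0.8, 1.0 | Type I error; σ = 0.5, 0.8, 1.0 |
|---|---|---|
| 5% | 43.8%, 42.4%, 41.9% | 0.081, 0.062, 0.058 |
| 10% | 47.5%, 44.7%, 43.7% | 0.171, 0.096, 0.079 |

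The spurious difference is 2.4 points (1.9 to 3.8) at 5% and 4.7 points (3.7 to 7.5) at 10%. Under-reading would bias the comparison the other way.

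**The case against.** The best reply is that the documents establish a risky order and silence about who knows the arm, not biased baselines. Only the project leader is said to open the envelope. The plan does not say that this person collects data, or that the patient, interviewer or assessor is told the result first. That stands: exposure is inferred. The introductory pages were also removed from the available text, so the absence of blinding is a statement about what can be read.

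The size of the effect rests on an assumed pattern. With no blinding described at weeks 4 and 8 either, a reporting shift could persist, and a shift constant over all visits cancels in a change score. The largest figures apply to an unadjusted change analysis, which 2.8 does not specify; a group effect averaged over the three visits gives only about 0.06 for a 0.1 SD shift and 0.08 to 0.09 for 0.2 SD. Section 2.8 also times the wound test from admission rather than baseline, so its use of the baseline area from 2.6.2 is the natural reading but not an explicit one. All of this limits how far the figures can be pressed.

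Finally, unmasked follow-up may be the larger source of bias. That may be so, but it is no reason to leave the baseline exposed when reordering the steps would protect it.

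**Conclusion.** The concern holds. As written, 2.7 collects the outcome baselines after the envelope is opened, and nothing in the available text prevents those recording them from knowing the arm. Whether any baseline is actually affected cannot be determined from the documents.

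The consequences depend on the effect tested. The 50% wound reduction is a change from baseline by definition and is exposed directly. For the questionnaire scores, the bias is the full shift in a change or group-by-time effect, ρ times the shift with baseline adjustment, one third of it (with reversed sign) in a three-visit average, and zero if only follow-up values are compared. Under the stated assumptions, inflation ranges from negligible to serious, and the figures illustrate sensitivity rather than estimate bias. The case for changing the plan rests on the order of steps and the low cost of correcting it. It should be fixed; confidence is medium because exposure is inferred.

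**What to change.** Reword 2.7 so that consent, stratum assignment, all baseline questionnaires and the baseline wound measurement are completed and locked before the next envelope for that stratum is opened. Keep weeks 4 and 8 counted from that baseline. State in the same place who is told the arm and when, in particular the interviewer and the wound assessor.

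For patients already enrolled (recruitment was planned from August 2023), record which order was followed, where this can be recovered. If it varied, add a sensitivity analysis by order, noting that order is confounded with calendar time. If everyone followed 2.7 as written, there is nothing to compare, and the order should be reported as a limitation for those patients.

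The cost is a wording change, the same steps in a different order, a little record-keeping and at most one extra analysis. No patients, visits or procedures are added. The reordering protects the baseline only; reporting bias at weeks 4 and 8 remains.
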